13 METHODS OF EFFICACY ANALYSES

In general, comparisons will be pairwise between ACP-044 400 mg Q6H, ACP-044 1600 mg QD and placebo.

13.1 Primary Efficacy Endpoints

13.1.1 Primary Analysis

The primary clinical question of interest for the primary objective is: what is the difference in the mean AUC_{0-24} of the NRS of pain intensity scores comparing ACP-044 400 mg Q6H vs. placebo and ACP-044 1600 mg QD vs. placebo, in subjects with acute postoperative pain following orthopedic surgery?

The estimand is described by the following attributes:

Population: Adult subjects that have acute postoperative pain following orthopedic surgery, as defined by the inclusion/exclusion criteria of the study.

Variables (Primary Endpoint): mean AUC_{0-24} of NRS pain intensity scores

Treatment Condition: ACP-044 400 mg Q6H, ACP-044 1600 mg QD and placebo, with use of rescue medications.

Intercurrent Events and Strategies:

- Treatment Discontinuation will be addressed by the hypothetical strategy, i.e., assuming that subjects with these intercurrent events (ICEs) continue to experience the following the distribution of worst observed pain prior to the ICE occurrence if they discontinue for lack of efficacy or an adverse event; subjects discontinuing for other reasons will be assumed to follow the distribution of values within their treatment group.
- Taking Rescue Medication will be addressed by the composite strategy of estimating pain scores in the presence of taking rescue medication by replacing assessments taken within a 4-hour window with the pre-rescue value. Should the NRS pain assessment taken immediately prior to rescue be less than a scheduled pain assessment, that scheduled pain assessment will be retained.

Alternative approaches to handling ICEs will be addressed in sensitivity analyses.

Population-level Summary Measure:

The treatment difference (ACP-044 400 mg Q6H vs placebo, ACP-044 1600 mg QD vs placebo) in the mean NRS pain intensity score AUC₀₋₂₄.

Hypotheses

The primary endpoint is AUC₀₋₂₄ based on the pain intensity scores from 0 to 24 hours assessed using NRS.

Let Δ_{auc_1} and Δ_{auc_2} be the difference between each of the two ACP-044 dose groups and placebo group in the mean AUC₀₋₂₄, respectively.

The null hypotheses are: $\Delta_{auc_i} = 0$ and the alternative hypothesis is: $\Delta_{auc_i} \neq 0$, $i=1,2$.

Primary Estimator

The hypothesis testing will be performed for the Full Analysis Set using analysis of variance (ANOVA) with treatment group and site as factors in the model. Prior to analysis, missing pain assessments will be imputed before calculating AUC per [Section 5.2.1](#). In addition, the AUC will have the last time point adjusted by as described in [Section 5.2.1.1](#).

The ANOVA results will be processed using the SAS MIANALYZE procedure to yield a combined estimate for treatment effect, standard error, and associated 95% confidence interval (CI) and p-value ([Rubin 1976](#)).

The treatment effect size, Cohen's d, will be presented for both ACP-044 comparisons to placebo using the following formula:

$$\text{Effect Size} = \frac{\text{LS mean difference}}{\text{Standard Deviation}}$$

Where Standard Deviation is approximated:

$$\text{Standard Deviation} = \frac{\text{Standard Error of LS mean Difference}}{\sqrt{\frac{1}{n_1} + \frac{1}{n_2}}}$$

And n_1 and n_2 are the sample sizes in each group. The sign (+ or -) of the effect size will be chosen so that a positive value favors ACP-044.

Summary statistics for the mean NRS pain intensity assessments (before and after single imputation) and the mean of AUC of pain intensity scores, the LS means, the between-group difference in LS mean with the corresponding confidence interval, p-value, and the effect size (Cohen's d) will be presented.

All pairwise treatment group comparisons will be presented.

A line plot of the mean (+/- the SE) NRS pain intensity assessments over time will be presented by treatment group.

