3.5 Determination of Sample Size

The planned sample size is 240 randomized subjects (80 subjects per treatment group).

Assuming a treatment difference in the AUC from 0 to 24 hours is 23 points between the ACP-044 groups and placebo group, and the common standard deviation is 50 points, 76 subjects per treatment arm will provide approximately 80% power to detect the assumed treatment difference using a t-test between each ACP-044 dose arm and placebo at a 2-sided significance level of 0.05. Assuming no more than 5% of randomized subjects will be excluded from primary efficacy analysis, 80 subjects per treatment group will be randomized.

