13.4 Exploratory Efficacy Endpoints

Proportion of subjects with severe pain (defined as an NRS pain intensity score ≥ 7 at any timepoint through 72 hours)

The proportion of subjects with severe pain will be analyzed using a stratified CMH test controlling for site.

The odds ratio, 95% confidence interval and p-values from the CMH test will be provided by treatment group pairwise.

Foot and Ankle Ability Measure (FAAM)

The summary of each movement category will be summarized descriptively as a categorical variable. The overall grades (ADL item score percentage, patient reported ADL overall score, Sports item score percentage, patient reported Sports overall score, and derived total score) will be summarized as a continuous variable. The change from baseline in overall grade will be analyzed using analysis of covariance (ANCOVA) with treatment group and site as factors and baseline (Day -1) FAAM as a covariate in the model.

The LS mean (SE), 95% confidence intervals, and p-values will be presented by treatment group. The LS mean difference (SE), associated 95% confidence intervals, p-values, and Cohen's d will be presented by treatment group pairwise.

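### For the AUC endpoints, the SD in Cohen's d is back-calculated from the pooled multiple-imputation SE, so it includes imputation variance and d shrinks as more post-dropout data are imputed

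*SAP*

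**What the plan says.** SAP 13.1.1 fits an ANOVA with treatment and site to each imputed dataset and then pools: "The ANOVA results will be processed using the SAS MIANALYZE procedure to yield a combined estimate for treatment effect, standard error", confidence interval and p-value. Cohen's d is the LS-mean difference over a standard deviation. That standard deviation, which the SAP labels an approximation, is the "Standard Error of LS mean Difference" divided by sqrt(1/n1+1/n2). No other SE is named, so for AUC0-24 the pooled SE goes into the formula. Appendix 21.2 sets the number of imputations at 50.

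SAP 13.3 analyses the other seven AUC endpoints like the primary. It also reports Cohen's d for rescue medication amount, pain-free hours and the global evaluation, each from a treatment + site ANOVA with no multiple imputation specified.

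For FAAM, SAP 13.4 says: "The change from baseline in overall grade will be analyzed using analysis of covariance (ANCOVA) with treatment group and site as factors", with baseline FAAM as covariate. It reports Cohen's d without giving a formula, and SAP 5.2.10 rules out imputation of FAAM.

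Cohen's d does not appear in the testing sequence of SAP 12.3.

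**The concern.** The standardizer in Cohen's d should describe how much patients differ. Under multiple imputation, the pooled SE carries a second component, the between-imputation variance, which measures uncertainty about scores that were never observed. Converting that SE back to an SD counts this uncertainty as patient spread. The reported d is then the pooled t-statistic times sqrt(1/n1+1/n2). It falls as more data are imputed, even if the mean difference and the patient spread stay the same.

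What is at stake is comparability. Protocol 1.5.2 says that the two regimens are tested so that the better one can be selected. Imputation is run separately by arm (Appendix 21.2), so two regimens with equal effects could show different values of d only because one had more dropout. AUC windows that end later would tend to be shrunk more, because dropout accumulates.

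**Working it through.** **Inputs from SAP 3.5.** "Assuming a treatment difference in the AUC from 0 to 24 hours is 23 points"; "the common standard deviation is 50 points"; "76 subjects per treatment arm will provide approximately 80% power"; the test is "at a 2-sided significance level of 0.05". From Appendix 21.2, m = 50.

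**The plan's own figure.** SE = 50 × sqrt(2/76) = 8.11, and 23/8.11 = 2.836. Normal-approximation power is Φ(2.836 − 1.960) = 0.809; the two-sample t-test gives 0.804. Also 76/0.95 = 80. The sample size reproduces, and the planning effect size is d = 23/50 = 0.46.

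**Complete data.** With n per arm and residual SD σ, SE = σ × sqrt(2/n). Dividing by sqrt(2/n) returns σ = 50 and d = 0.46. The formula works, provided arms are balanced within sites, which site-stratified randomization makes nearly true.

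**With multiple imputation.** Let W be the mean within-imputation variance of the difference and B the between-imputation variance.
- Total variance: T = W + (1+1/m)B.
- SAP standardizer: sqrt(T)/sqrt(1/n1+1/n2) = σ × sqrt(1+r), with r = (1+1/m)B/W.
- With λ = (1+1/m)B/T, the share of total variance due to imputation, r = λ/(1−λ) and d(SAP) = d × sqrt(1−λ).

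The documents give no dropout rate and no λ, so λ is an assumption:

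| λ | r | SD by SAP formula | d by SAP formula |
|---|---|---|---|
| 0 | 0 | 50.0 | 0.460 |
| 0.02 | 0.020 | 50.5 | 0.455 |
| 0.05 | 0.053 | 51.3 | 0.448 |
| 0.10 | 0.111 | 52.7 | 0.436 |

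**Simulation check.** Three arms of 80, three sites, m = 50, no site variance, whole AUCs missing at random and imputed within arm from a predictor correlated 0.5 with the AUC. With 5%, 10% and 20% of AUCs missing, λ was 0.043, 0.087 and 0.168. The SAP standardizer was 51.3, 52.8 and 55.6, against within-imputation SDs of 50.2, 50.4 and 50.7. So d was about 2%, 4.5% and 9% low.

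**Choice of reference SD.** The ANOVA also removes between-site variance. If site accounts for a share s of the AUC variance (assumed), d(SAP) relative to d on the raw pooled within-arm SD is sqrt((1−λ)/(1−s)):
- λ = 0.05, s = 0: 0.975
- λ = 0.05, s = 0.05: 1.00
- λ = 0.05, s = 0.10: 1.03

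The simulation with 5% of AUCs missing gave 1.00 at s = 0.05 and 1.04 at s = 0.10.

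**FAAM.** If the 13.1.1 formula is applied, the standardizer is the residual SD after baseline adjustment. Assume equal variances τ² at baseline and follow-up, and correlation ρ between them. Then:
- residual SD = τ × sqrt(1−ρ²)
- change-score SD = τ × sqrt(2(1−ρ))
- ratio of d on the residual SD to d on the change-score SD = sqrt(2/(1+ρ)), which is 1.24, 1.15 and 1.08 at ρ = 0.3, 0.5 and 0.7.

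No correlation is given in the documents, so these values of ρ are also assumptions.

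**The case against.** The SAP calls the SD an approximation, d decides nothing, and the LS-mean difference and summary statistics for the AUC are reported, so a reader can standardize by an ordinary SD. All true, and it is why this is a minor point. But the departure is systematic, and no approximation is needed: every ANOVA fit supplies its residual mean square.

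Four stronger readings are tempting, and the documents do not support them.

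- *A next trial sized on this d would be too large.* For a trial with the same missingness and the same imputation analysis, power depends on T, which is what the formula recovers. Sizing on the within-imputation SD alone would underpower it: at 76 per arm, power is Φ(2.836 × sqrt(1−λ) − 1.960), about 0.79 at λ = 0.05 and 0.77 at λ = 0.10, against 0.81. Oversizing follows only if a separate dropout inflation is then added.
- *The 5% in the sample-size section gives the amount imputed.* That sentence reads "Assuming no more than 5% of randomized subjects will be excluded from primary efficacy analysis". It concerns exclusions, not dropouts whose scores are imputed. Moreover, SAP 5.2.1 interpolates intermediate gaps and gives a missing time-0 score a single mean. Appendix 21.2 lets imputation fill only scores after dropout. A patient who leaves at hour 18 keeps 18 of the 24 hours as observed. With an inpatient stay and site-observed dosing, λ is probably at the low end of the table.
- *d for the AUCs is simply too small.* That holds against the within-site residual SD. Against the raw pooled SD, the site adjustment can cancel or reverse it.
- *Every reported d is affected.* Rescue amount, pain-free hours and the global evaluation use ANOVA without imputation, and the formula serves them adequately.

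For FAAM, applying the formula is an inference from the absence of another. An SD adjusted for baseline is also a defensible choice, and it is the relevant one for planning a trial that repeats the ANCOVA. The issue there is labelling.

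**Conclusion.** The point holds for the AUC endpoints. As written, their standardizer is the within-site residual SD times sqrt(1+r), so d depends on how much was imputed. The size is small: 0.46 becomes about 0.455, 0.448 or 0.436 if imputation supplies 2%, 5% or 10% of the total variance. All three shares are assumed, and a loss of about 2% of d or less is the likely outcome. The direction is relative to the within-site residual SD only.

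For FAAM, if the same formula is used, d is on a baseline-adjusted scale. It is larger than d on the change-score SD by about 24%, 15% or 8% at assumed correlations of 0.3, 0.5 or 0.7 with equal variances. That part is secondary, because the use of the formula is inferred and the choice of SD is open.

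Nothing confirmatory is touched: the treatment estimates, confidence intervals, p-values, testing sequence and sample size stand.

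**What to change.** In SAP 13.1.1, for AUC endpoints, define the SD in Cohen's d as the square root of the treatment + site ANOVA residual mean square averaged over the 50 imputations, and state that it is a within-site SD. Keep the pooled LS-mean difference as numerator. Endpoints analysed by ANOVA without imputation need no change.

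In SAP 13.4, either label the FAAM d as baseline-adjusted or standardize by the SD of the change score, and say which.

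The cost is one or two sentences in the SAP and a small programming change. The residual mean square is already available from each fit, and no new data or analysis is needed.

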13.1.2 Sensitivity Analyses

The following sensitivity analyses of the primary efficacy endpoint are planned to describe different strategies for intercurrent events.

13.1.2.1 Alternative Handling of Rescue Medication Censoring

As an alternative strategy to the intercurrent event of taking rescue medication, the impact of the censoring described in [Section 5.2.1](#) will be investigated a few different ways:

1. A 2 hour censoring window will be used.
2. A 6 hour censoring window will be used.
3. No values will be censored for use of rescue medication.

For each of the above scenarios, the other components of the imputation and data handling will be identical to the primary and the NRS pain intensity score AUC_{0-24} values will then be calculated, and analyzed similarly as in the primary analysis.

13.1.2.2 Multiple Imputation Variations

As a sensitivity to the primary endpoint analysis, the multiple imputation approach will be adjusted to better understand the impacts of its assumptions. Four approaches will be investigated:

1. All subjects, regardless of reason for withdrawal, will have missing data imputed under a missing-at-random assumption within treatment groups.
2. All subjects, regardless of reason for withdrawal, will have missing data imputed using the distribution of the worst values through that point.
3. Subjects that withdraw due to “other” and “unknown” reasons will be grouped with those that withdraw for LOE and AEs; all other imputation rules from the primary analysis will be unchanged.
4. In addition, the placebo-based imputation will be applied to the missing data due to AE or LOE. Like “standard” multiple imputations, except parameters for imputation model will be obtained from only the placebo (control) group. Both placebo and drug groups will be imputed based on the imputation model derived from placebo data. If drug improves outcomes prior to dropout, this benefit is carried into subsequent imputed values, but will diminish over time in accordance with the correlation structure. Subjects that discontinue for reasons other than LOE or AE will have their values imputed within treatment group with MI assuming MAR with covariates for all observed time points.

13.1.3 Supportive Analyses

Supportive analysis of the primary efficacy endpoint **may** be analyzed in a similar fashion as the primary analysis, using the Per-Protocol analysis set.

13.2 Key Secondary Efficacy Endpoints

Analysis of the key secondary efficacy endpoints will be performed using the Full Analysis Set.

Time to first rescue medication use after time 0 (hours)

A stratified log-rank test stratified by site will be used to compare the time to first rescue medication use after time 0 by treatment group. The follow-up time will end at 72 hours. The time at which subjects discontinue due to the lack of efficacy will be considered as an event. Subjects who do not take rescue medication and who do not discontinue for lack of efficacy will be censored at 72 hours or their last follow-up time, whichever is earlier. The estimate and 95% CI's for the median time to event will be summarized by treatment group, where

event is the time to first rescue medication use after time 0. The p-value of the stratified test of equality over treatment group for each pairwise comparison will be summarized.

Sample SAS code:

```
proc lifetest data=indata;
  time time*cnsr(1);
  strata site /group=trt;
run;
```

where time is the time to first rescue or censor, cnsr is the censor status, site is the site variable, and trt is the treatment group variable.

In addition, a stratified by site Cox proportional hazards model treatment group as a factor will be used to analyze the time to rescue medication or censoring. The follow-up time will end at 72 hours. The time at which subjects discontinue due to the lack of efficacy will be considered as an event. Subjects who do not take rescue medication and who do not discontinue for lack of efficacy will be censored at 72 hours or their last follow-up time, whichever is earlier.

The hazard ratio and 95% confidence interval will be summarized for each pairwise comparison as defined previously.

Kaplan-Meier curves of time to first rescue will be presented.

Sample SAS code:

```
proc phreg data=indata covsandwich;
  class trt(ref="Placebo");
  model time*cnsr(1)= trt/ ties=exact;
  strata site;
run;
```

In addition, the number and percentage of subjects taking rescue medication or discontinuing due to lack of efficacy and the number and percentage of subjects censored will be summarized.

Proportion of subjects who were opioid free through 24, 48, and 72 hours

The proportion of subjects who are opioid free (did not take acetaminophen-hydrocodone oral tablet as rescue medication or any other opioid) through 24, 48, and 72 hours and during 0-<24 hours, 24-<48 hours, and 48-72 hours will be analyzed using a stratified CMH test controlling for site.

The risk difference, 95% confidence interval and p-values will be provided by treatment group pairwise.

13.3 Secondary Efficacy Endpoints

Analyses of the secondary efficacy endpoints will be performed using the Full Analysis Set.

The following secondary efficacy endpoints will be analyzed similarly as the primary analysis for the primary efficacy endpoint.

- The mean AUC₀₋₄₈ of NRS of pain intensity scores

- The mean AUC_{0-72} of NRS of pain intensity scores
- The mean AUC_{0-4} of NRS of pain intensity scores
- The mean AUC_{0-6} of NRS of pain intensity scores
- The mean AUC_{0-12} of NRS of pain intensity scores
- The mean AUC_{24-48} of NRS of pain intensity scores
- The mean AUC_{48-72} of NRS of pain intensity scores

Amount of rescue medication taken during 0-24, 24-48, 48-72, 0-48, and 0-72 hours

The following will be summarized:

- The number of tablets of ibuprofen taken during 0-24, 24-48, 48-72, 0-48, and 0-72 hours.
- The number of tablets acetaminophen-hydrocodone taken during 0-24, 24-48, 48-72, 0-48, and 0-72 hours.
- The number of instances of any rescue medication taken during 0-24, 24-48, 48-72, 0-48, and 0-72 hours.
- The amount of opioids in Morphine Milligram Equivalents (MME) taken during 0-24, 24-48, 48-72, 0-48, and 0-72 hours

Each of the above items will be analyzed using ANOVA with treatment group and site as factors in the model by rescue medication type.

The LS mean (SE), 95% confidence intervals, and p-values will be presented by treatment group. The LS mean difference (SE), associated 95% confidence intervals, p-values, and Cohen's d will be presented by treatment group pairwise.

Proportion of subjects who did not use rescue medication through 24, 48, and 72 hours

Given the in-clinic setting of this study, subjects with no records of rescue medication dispensation will be assumed to not have used any rescue medication.

The proportion of subjects who did not use rescue medication (neither acetaminophen-hydrocodone oral tablets nor ibuprofen nor any other) through 24, 48, and 72 hours will be summarized and will be analyzed using a stratified Cochran-Mantel-Haenszel (CMH) test controlling for site.

The risk difference, 95% confidence interval and p-values will be provided by treatment group pairwise.

Proportion of subjects who were opioid free during 24-48 hours and 48-72 hours

The proportion of subjects who are opioid free (did not take acetaminophen-hydrocodone oral tablet as rescue medication or any other opioid) through 24, 48, and 72 hours and during 0-<24 hours, 24-<48 hours, and 48-72 hours will be analyzed using a stratified CMH test controlling for site.

The risk difference, 95% confidence interval and p-values will be provided by treatment group pairwise.

Proportion of subjects who are pain free (NRS <2) at 24, 48, and 72 hours

The proportion of subjects who are pain free at 24, 48, and 72 hours will be analyzed using a stratified CMH test controlling for site.

The risk difference, 95% confidence interval and p-values will be provided by treatment group pairwise.

Number of hours subjects are pain free (NRS <2)

The number of hours subjects are pain free will be analyzed using ANOVA with treatment group and site as factors in the model. Each active dose group will be compared to placebo using this model.

The LS mean (SE), 95% confidence intervals, and p-values will be presented by treatment group. The LS mean difference (SE), associated 95% confidence intervals, p-values, and Cohen's d will be presented by treatment group pairwise.

Global evaluation of study drug just before time of first rescue and at the end of 24, 48, and 72 hours

The global evaluation of study drug (GESD) will be summarized as a categorical and as a continuous variable for each visit and for each censoring approach:

- With all values reported as recorded
- With values following rescue censored
- With the pre-rescue values grouped with the subsequent time point and values following rescue censored

The GESD will be analyzed by visit using ANOVA with treatment group and site as factors in the model.

The LS mean (SE), 95% confidence intervals, and p-values will be presented by treatment group. The LS mean difference (SE), associated 95% confidence intervals, p-values, and Cohen's d will be presented by treatment group pairwise.

13.4 Exploratory Efficacy Endpoints

Proportion of subjects with severe pain (defined as an NRS pain intensity score ≥ 7 at any timepoint through 72 hours)

The proportion of subjects with severe pain will be analyzed using a stratified CMH test controlling for site.

The odds ratio, 95% confidence interval and p-values from the CMH test will be provided by treatment group pairwise.

Foot and Ankle Ability Measure (FAAM)

The summary of each movement category will be summarized descriptively as a categorical variable. The overall grades (ADL item score percentage, patient reported ADL overall score, Sports item score percentage, patient reported Sports overall score, and derived total score) will be summarized as a continuous variable. The change from baseline in overall grade will be analyzed using analysis of covariance (ANCOVA) with treatment group and site as factors and baseline (Day -1) FAAM as a covariate in the model.

The LS mean (SE), 95% confidence intervals, and p-values will be presented by treatment group. The LS mean difference (SE), associated 95% confidence intervals, p-values, and Cohen's d will be presented by treatment group pairwise.

